**1. AMENDMENT HISTORY**

Amendment No.	Protocol Version No.	Date issued	Author(s) of changes	Details of Changes made
1	2	1/1/17	[name] and [name]	APPENDIX A: STUDY FLOWCHART Time line edited to allow more time to recruit.

List details of all protocol amendments here whenever a new version of the protocol is produced.

2. SYNOPSIS

Study Title	Serum blood clotting changes during blood sampling via non-luer one-way filter valve intravenous needle: Implication on the epidural blood patch procedure
Internal ref. no.	
Trial Design	Observational Study
Trial Participants	Healthy post natal and non-pregnant participants
Planned Sample Size	Total 50 participants
Follow-up duration	n/a
Planned Trial Period	12 months
Primary Objective	Investigate clotting profile changes due to the use of the new non-luer one-way valve filter needle compared to a standard hypodermic needle.
Secondary Objectives	n/a
Primary Endpoint	Analysis of blood via near patient TEG clotting analysis

3. ABBREVIATIONS

AE	Adverse event
AR	Adverse reaction
CI	Chief Investigator
CRA	Clinical Research Associate (Monitor)
CRF	Case Report Form
CRO	Contract Research Organisation
CT	Clinical Trials
EC	Ethics Committee (see REC)
GCP	Good Clinical Practice
GP	General Practitioner
GTAC	Gene Therapy Advisory Committee
ICF	Informed Consent Form
NHS	National Health Service
NRES	National Research Ethics Service
PI	Principal Investigator
PIL/S	Participant/ Patient Information Leaflet/Sheet
R&D / R&I	NHS Trust Research &Development / Innovation Department
REC	Research Ethics Committee
SAE	Serious Adverse Event
SAR	Serious Adverse Reaction
SOP	Standard Operating Procedure
SUSAR	Suspected Unexpected Serious Adverse Reactions
TMF	Trial Master File

4. BACKGROUND AND RATIONALE

Patient safety agencies such as the National Patient Safety Agency (NPSA) and European Medicines Agency recommend adoption of equipment that prevents wrong route drug administration¹. For example medicine intended for the intravenous route should not be possible to be given via the epidural route, hence limiting potentially catastrophic complications associated with human error². However, the epidural blood patch requires equipment that connects to the intravenous and epidural route, as blood is taken from a patient's vein and then it is injected into the patient's epidural space for therapeutic effect. Hence equipment is required that allows blood aspiration from the patient but does not have the potential to inject into the patient hence complying with patient safety agency recommendations. Aspirating blood from the patient via a non-Luer one-way filter valve has the theoretical potential of activating the clotting cascade. If this occurred it could reduce the time the clinician has to utilise the blood before it clots in the syringe. Changes in clotting characteristics also has unknown implications when injected into the epidural space with regards to the therapeutic effect of the procedure.

The epidural blood patch is mainly used in obstetric anaesthesia in the treatment of dural puncture headaches, however it is also used to treat conditions such as spontaneous intracranial hypotension, hence this study involves post natal and non-pregnant populations. This study requires blood to be taken from the study participants via a venepuncture. This will require 12mls of blood to be taken from the patient via a standard 21G hypodermic needle and also 2mls of blood via the new 21G non-Luer one-way filter valve needle. The blood will undergo clotting profile testing. The implications for study subjects would be two venepunctures and a total of 14mls of blood taken. The post natal population would only require one additional venepuncture with the new one-way valve needle as they would already be having bloods taken for their day 2 post elective cesarean section bloods, an additional 9ml of blood only.

5. OBJECTIVES

5.1 Primary Objectives

We aim to determine if there is a difference in the clotting profile values from blood extracted with a normal 21G hypodermic needle vs the new 21G non-Luer one-way filter valve needle.

5.2 Secondary Objectives

Not Applicable

6. STUDY DESIGN

6.1 Summary of Trial Design

This study will be an observational study. The pregnant participants will be recruited from the elective pre-operative caesarean clinic and have their bloods taken on day 2 post natal after their elective caesarean section during their routine full blood count testing.

The healthy non-pregnant participants will be recruited via posters in the University Hospitals of Leicester.

The blood taken via the two different needles will be analysed via near patient testing with Thromboelastography (TEG) analysis and this will be the end of their study participation.

We will alternate between patients with regards to which needle will be used first during phlebotomy (ie hypodermic needle vs new non-Luer one-way valve filter needle). The punctures will be from separate veins for each of the two needles.

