8.4 Randomisation and Codebreaking (if applicable)

All participants will have a paired set of bloods taken with a hypodermic needle and the new one way valve filter needle. We will alternate which needle is used first between patients.

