10.1.5 Expected Serious Adverse Events/Reactions

This study is not expected to cause any serious adverse events or reactions. The main issues to note would be difficult phlebotomy which would be uncomfortable and phlebotomy can lead to bruising. None of these would require reporting.

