11. STATISTICS

11.1 Description of Statistical Methods

The primary outcome for this study is change in time to initiate clot formation, as measured by the R time using thromboelastography. As subjects are to be exposed to both study limbs the data collected will be analysed using paired tests for statistical differences. The variation is different for non-pregnant and post natal subjects, therefore we have calculated sample size for each of the two study populations separately. As the sample size is small it is unlikely that the results will be normally distributed, therefore non-parametric test will be employed. As the sample sizes are small we do not anticipate needing any interim analysis. There is no plan to compare non-pregnant and post natal groups, only the within group differences.

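### Needle order is alternated but vein is not assigned, so if operators choose the vein by needle, a vein effect on R time would be counted as a needle effect

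*Combined protocol and SAP*

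**What the plan says.** Section 6.1 sets the order rule, "We will alternate between patients with regards to which needle will be used first during phlebotomy", and then the site rule, "The punctures will be from separate veins for each of the two needles". Section 8.4, the only section on allocation, says "All participants will have a paired set of bloods taken with a hypodermic needle and the new one way valve filter needle" and "We will alternate which needle is used first between patients". It says nothing on vein, arm, operator or masking.

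Section 4 gives the draws unequal roles: "This will require 12mls of blood to be taken from the patient via a standard 21G hypodermic needle and also 2mls of blood", the 2 ml coming through the new needle. For the women after caesarean section it adds "The post natal population would only require one additional venepuncture with the new one-way valve needle", because the standard-needle draw is tied to their routine day 2 bloods.

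Section 11.1 states "The primary outcome for this study is change in time to initiate clot formation, as measured by the R time using thromboelastography". The analysis is a paired non-parametric test within each group, with no term for vein, order or puncture quality.

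The demographic items listed in 8.2 are age, gender, days post natal and blood loss; medication is also recorded. Vein, side and number of attempts are not listed. Section 10.1.5 says "The main issues to note would be difficult phlebotomy which would be uncomfortable and phlebotomy can lead to bruising" and adds that these need no reporting. Section 10.2 nevertheless has all adverse events entered on the CRF.

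**The concern.** Each pair compares one needle in one vein with the other needle in another vein. Pairing removes differences between people, but not differences between the two veins of the same person. The plan balances draw order and leaves open the second factor that its own site rule creates.

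The vein could plausibly follow the needle. The two needles differ physically, and alternation tells the operator which is due next. The standard needle also takes six times the volume (12 ml against 2 ml) and, in post natal women, supplies the clinically needed sample. An operator might reasonably keep the easier vein for it, whichever needle goes first.

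The only planned contrast is the within-person difference in R time. If a poorer puncture shortens R time, giving the new needle the poorer vein would imitate the effect the study looks for. Giving it the better vein would hide a real effect.

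**Working it through.** **1. The plan's own figure.** Section 11.2 gives 10 non-pregnant and 30 post natal participants for a 25% reduction in R time, alpha 5%, power 80%. These numbers cannot be reproduced, because neither the SD of the paired difference nor the mean R time is stated. They can be inverted. Sidedness is not stated in 11.2 or 11.3; two-sided is assumed here. By the normal approximation:

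- n = (SD × (1.960 + 0.842) / 25)², so SD = 25 × √n / 2.802, as a percentage of mean R time.
- n = 10: 25 × 3.162 / 2.802 = 28.2%.
- n = 30: 25 × 5.477 / 2.802 = 48.9%.
- In both groups the standard error is SD / √n = 25 / 2.802 = 8.92%, so one set of results serves both.

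**2. The bias.** Let p be the share of participants whose new needle gets the poorer vein, and d the shortening of R time in that vein. Neither is in the documents. The vein contributes −d to the new-minus-standard difference with probability p, and +d with probability 1 − p. Its mean is −d × p + d × (1 − p) = −(2p − 1) × d, that is, an apparent shortening of (2p − 1) × d. The sample size does not appear in it.

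**3. Which operator habits produce it.**

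- Better vein always used first: with order alternated, the new needle gets the poorer vein in 5 of 10 or 15 of 30 participants. Then p = 0.5 and the bias is zero for any d.
- Better vein always kept for the standard needle: p = 1 whichever needle goes first, and the bias is d.
- A mixture of habits falls between.

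The documents do not say which habit applies.

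**4. Size, for illustration.** With d = 10% and s = bias / 25 × 2.802:

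- False-positive rate with no needle effect = P(Z > 1.960 − s) + P(Z < −1.960 − s).
- Power when the bias opposes a true 25% reduction = P(Z > 1.960 − (2.802 − s)).

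| p | Bias | s | False-positive rate | Power if bias of this size opposes a true effect |
|---|---|---|---|---|
| 0.5 | 0% | 0 | 5% | 80% |
| 0.65 | 3% | 0.336 | 6.3% | 69% |
| 0.8 | 6% | 0.672 | 10.3% | 57% |
| 1 | 10% | 1.121 | 20.2% | 39% |

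For the last row, P(Z > 0.839) + P(Z < −3.081) = 0.201 + 0.001 = 0.202. The power column applies when the pairing runs the other way, that is at p = 0.35, 0.2 and 0 for the lower three rows.

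**5. Check with a rank test.** The setting was a two-sided Wilcoxon signed-rank test at 5%, no needle effect and 4,000 simulated trials per case. Residual SD was 25.1% (n = 10) or 47.2% (n = 30), the values a paired t calculation implies. At d = 10% and p = 1 the false-positive rate was about 20% (n = 10) and 19% (n = 30). At p = 0.75 (bias 5%) it was about 8% in both. With veins balanced between needles it was at most 5%.

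**The case against.** The case against is substantial.

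- **The mechanism is not in the documents.** Section 4 raises activation of clotting only for aspiration through the filter valve. Nothing says that a poor puncture shortens R time. If d is negligible, vein allocation does not matter.
- **A common habit would already be balanced.** Using the best vein for the first puncture is at least as natural as keeping it for one needle, and the alternation then does its work. The routine-sample motive applies only to the post natal group; for volunteers only the volume difference remains.
- **Some information would be kept.** Section 10.1.5 concerns safety reporting and does not forbid recording. Under 10.2, bruising or a puncture bad enough to count as an adverse event would reach the CRF.
- **The illustration rests on chosen values.** The mildest case moves the false-positive rate only from 5% to 6.3%, and the 20% figure needs the new needle always to get the poorer vein.

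All of this stands, and it rules out three stronger readings that a reader might infer. The documents do not show that the easier vein will go to the standard needle, that the R-time comparison is in fact biased, or that the matter could never be examined afterwards. The objection does not supply a rule linking vein to order or needle, or any concealment of the next needle. Nor does it supply a vein or attempt count for each needle.

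**Conclusion.** The plan leaves the pairing of vein and needle open. A needle-dependent choice of vein would then bias its only planned contrast if vein or puncture quality affects R time. The direction and size are unknown. On the assumptions above (two-sided test, normal approximation, d = 10%), the false-positive rate runs from about 6% to 20% as p goes from 0.65 to 1, and stays at 5% if p = 0.5. Operator freedom and knowledge of the needle are inferred from the plan's silence, though nothing in the text contradicts them. This is a weakness in allocation that is cheap to close before recruitment, not evidence that the result would be wrong.

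**What to change.** In 6.1 and 8.4, replace the open alternation with a concealed, balanced order list, for example sealed envelopes in blocks within each group. Suggested text:

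*The operator selects and ranks two veins before the needle order is revealed. The first draw is taken from the first-ranked vein and the second draw from the second-ranked vein, whichever needle is due.*

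Add three CRF fields for each needle: vein and side, draw position, and number of attempts.

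Concealment is needed. If the order stayed predictable, an operator who knew which needle was due could rank the veins to suit it, and p = 0.5 would not be secured. Ranking first and tying vein to draw position lets a balanced order list balance vein as well. There is no need to require the same operator for both draws, since the documents do not say who takes the routine day 2 sample.

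The cost is preparing the envelopes, a short protocol change and the CRF fields. It adds no puncture, blood or participants, and the numbers of 10 and 30 stay as they are. In about half of participants the larger draw would come from the second-ranked vein. Replacement of withdrawn participants (8.7) and exclusion of spurious data (11.5) may leave a slight imbalance among analysed pairs, which the recorded fields would allow to be checked.

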6.2 Primary and Secondary Endpoints/Outcome Measures

Blood taken by each needle from the participants will undergo near patient TEG analysis and we will be investigating the difference in R-Time, the time for a clot to form. The blood will also be sent for laboratory full blood count and clotting profile testing.

7. TRIAL PARTICIPANTS

7.1 Overall Description of Trial Participants

We will enrol pregnant participants who are due to have an elective caesarean section and have no medical condition. Non-pregnant participants will be healthy volunteers.

7.2 Inclusion Criteria

Participant is willing and able to give informed consent for participation in the study.

Male (in the volunteer subgroup) or Female.

Aged 18 years or above.

Within first 2 days post natal for post natal arm of study

Healthy participants must be in good health.

Able (in the Investigators opinion) and willing to comply with all study requirements.

Willing to allow his or her General Practitioner and consultant, if appropriate, to be notified of participation in the study.

7.3 Exclusion Criteria

The participant may not enter the study if ANY of the following apply:

Any medical condition

Post natal women with haemorrhage greater than 1L

Less than 12 hours post prophylactic dalteparin

Any clotting abnormality

On any medication including herbal medication (vitamins taken in pregnancy are acceptable)

Age less than 18 years at recruitment

Adults who are not capable of giving valid consent

Adults with learning disabilities/ difficulties

Adults in emergency situations

Unable to speak or read English

Prisoners

Adults unable to consent for themselves

Any person considered to have a particularly dependent relationship with investigators

Any others deemed to belong to a vulnerable group.

Any other significant disease or disorder which, in the opinion of the Investigator, may either put the participants at risk because of participation in the study, or may influence the result of the study, or the participant's ability to participate in the study.

Participants who have participated in another research study involving an investigational product in the past 12 weeks

8. STUDY PROCEDURES

8.1 Informed Consent

The participant must personally sign and date the latest approved version of the informed consent form before any study specific procedures are performed.

Written and verbal versions of the participant information and Informed consent will be presented to the participants detailing no less than: the exact nature of the study; the implications and constraints of the protocol; the known side effects and any risks involved in taking part. It will be clearly stated that the participant is free to withdraw from the study at any time for any reason without prejudice to future care, and with no obligation to give the reason for withdrawal.

The participant will be allowed as much time as wished to consider the information, and the opportunity to question the Investigator, their GP or other independent parties to decide whether they will participate in the study. Written Informed Consent will then be obtained by means of participant dated signature and dated signature of the person who presented and obtained the informed consent. The person who obtained the consent must be suitably qualified and experienced, and have been authorised to do so by the Chief/Principal Investigator as detailed on the Delegation of Authority and Signature log for the study. The original signed form will be retained at the study site within the Trial Master File (TMF) or Investigator Site File (ISF). A copy of the signed Informed Consent will be given to participants and a copy retained in the participant medical notes.

8.2 Screening and Eligibility Assessment

Pregnant participants will be identified in preoperative clinics for elective caesarean sections. Medical notes will be screened to recruit healthy volunteers.

Non-pregnant healthy participants will be recruited via poster advertisement placed within University Hospitals of Leicester.

Demographics

The age, gender, days post natal for pregnant women and blood loss will be recorded.

Medical History

We would only recruit participants who do not have any medical conditions.

Concomitant Medication

All over-the-counter or prescription medication, vitamins, and/or herbal supplements will be recorded on CRFs.

8.3 Baseline Assessments

No baseline assessments are required for this research project.

8.4 Randomisation and Codebreaking (if applicable)

All participants will have a paired set of bloods taken with a hypodermic needle and the new one way valve filter needle. We will alternate which needle is used first between patients.

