8.6 Definition of End of Trial

The end of trial will be the completion of the 30th paired TEG test in the pregnant group and the 10th in the volunteer group.

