8.7 Discontinuation/Withdrawal of Participants from Study Treatment

Each participant has the right to withdraw from the study at any time. In addition, the investigator may discontinue a participant from the study at any time if the investigator considers it necessary for any reason including:

Ineligibility (either arising during the study or retrospective having been overlooked at screening)

Significant protocol deviation

Significant non-compliance with treatment regimen or study requirements

An adverse event which requires discontinuation of the study or results in inability to continue to comply with study procedures

Developing a medical condition

Consent withdrawn

Lost to follow up

If participants are withdrawn from the study they will be replaced and data acquired from withdrawn participants will be destroyed. The reason for withdrawal will be recorded in the CRF.

If the participant is withdrawn due to an adverse event, the investigator will arrange for follow-up visits or telephone calls until the adverse event has resolved or stabilised.

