11.3 The Level of Statistical Significance

Alpha error of 5%, beta error 20%, power 80%

11.4 Criteria for the Termination of the Trial.

The trial will be terminated when 10 non-pregnant volunteers and 30 post natal volunteers have completed the study protocol.

11.5 Procedure for Accounting for Missing, Unused, and Spurious Data.

The trial will be terminated once we have 40 complete data sets. There will be no unused data sets. Spurious data will be excluded from analysis and will require additional recruitment.

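### Does needle-order alternation have to be tied to each analysed group, and to replacements, for the comparison to be sound?

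*Combined protocol and SAP*

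**What the plan says.** Two places in the protocol set the order rule. Section 6.1 says "We will alternate between patients with regards to which needle will be used first during phlebotomy", and adds that each needle uses a separate vein. Section 8.4 says "We will alternate which needle is used first between patients". Neither says whether there is one list for the study or one per group.

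The analysis is by group. Section 11.1 specifies paired non-parametric tests and states "There is no plan to compare non-pregnant and post natal groups, only the within group differences". Section 8.6 ends the trial at "completion of the 30th paired TEG test in the pregnant group and the 10th in the volunteer group".

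Losses are made good. Section 8.7 says "If participants are withdrawn from the study they will be replaced and data acquired from withdrawn participants will be destroyed". Section 11.5 says "Spurious data will be excluded from analysis and will require additional recruitment" and "The trial will be terminated once we have 40 complete data sets". None of these sections mentions the order slot of the person replaced. The Synopsis gives "Total 50 participants", against the 40 complete sets of section 11.5. The documents do not explain the difference.

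**The concern.** Each participant is sampled with both needles, so anything that differs between first and second venepuncture could be mistaken for a needle effect. Alternation removes this from the mean paired difference only if the two orders are equally frequent in the group being analysed. A list balanced over all 40 participants can be unbalanced among the 10 volunteers. A replacement who takes the next free slot, rather than the lost one, can also upset the balance.

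If order does affect R time, an uneven split would bias the needle estimate. The volunteers are the more exposed group: under a shared list a given excess of one order is the same count in both groups, and so three times as large a share of 10 as of 30.

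**Working it through.** **Inputs.** From section 11.2: 10 volunteers and 30 post natal women, a 25% reduction in R time, alpha 5%, power 80%. Not given: the SD of the paired difference, sidedness, the named test and any order effect. Assumed: two-sided test, normal differences, Wilcoxon signed-rank test.

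**The plan's own figure.** The sample sizes cannot be reproduced without the SD, so it was back-solved. A paired t-test with 80% power needs a standardised effect d = 0.996 at n = 10 and 0.529 at n = 30. The implied SDs are 25/0.996 = 25.1% and 25/0.529 = about 47% of mean R. With d = 0.996 and no order effect, the signed-rank test has 78% power at n = 10.

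**Bias.** Let order shift the paired difference by +w in n1 participants and −w in n2. The mean difference is then biased by w(n1 − n2)/n.

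- Volunteers: 6:4 gives 2/10 = 20% of w; 7:3 gives 4/10 = 40%.
- Post natal: 16:14 gives 2/30 = 6.7% of w; 17:13 gives 4/30 = 13.3%.

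Write w = f × 25% of mean R. At 6:4, f = 0.25 gives 0.20 × 6.25% = 1.25% of mean R, which is 5% of the target. At f = 0.50 the bias is 0.20 × 12.5% = 2.5% of mean R, or 10% of the target. The last case is extreme: the two orders then differ by 2 × 12.5% = 25% of mean R, as much as the whole target effect.

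**Power in the volunteers** (100,000 simulations; bias against / in favour of the needle effect, then the average):

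| f | 5:5 | 6:4 | 7:3 |
|---|---|---|---|
| 0.10 | 77.7% | 76.2 / 79.3, average 77.8% | 74.4 / 80.9, average 77.7% |
| 0.25 | 76.1% | 71.9 / 80.1, average 76.0% | 67.5 / 83.8, average 75.7% |
| 0.50 | 69.6% | 60.5 / 78.4, average 69.5% | 51.0 / 85.7, average 68.4% |

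The direction of any order effect is unknown, so the average is the fair comparison. It falls by at most 69.6 − 68.4 = 1.2 points. The drop from 78% to about 70% at f = 0.50 occurs at perfect 5:5 as well, because the order effect adds spread to the differences. Restoring balance would not recover it.

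**How likely an uneven split is, with one list per group.** Suppose replacements take the next slot, and losses fall at random among all but the last enrolled, who completes by definition.

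- One volunteer lost: 6:4 with probability 5/10 = 0.50.
- Two lost: 6:4 with probability [C(6,2) + C(5,2)]/C(11,2) = 25/55 = 0.45. Nothing worse is possible.
- Three lost: 7:3 with probability C(6,3)/C(12,3) = 20/220 = 0.09.

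These are conditional on losses that use up a slot. Section 6.1 applies the alternation at phlebotomy, so a woman recruited in clinic who drops out before her day 2 sample need not use one. Participation ends with the sample and its TEG test, so the relevant losses are mainly spurious results.

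**One shared list, volunteers at random positions.** The number of volunteers in one order is hypergeometric (40, 20, 10). P(5:5) = C(20,5)²/C(40,10) = 0.284. P(7:3 or worse) = 0.273. P(8:2 or worse) = 0.065. If the volunteers are instead sampled in one run, the same list gives 5:5.

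**Type I error in the volunteers.** For f from 0.10 to 0.50 it is 3.7–4.9% at 6:4 and 4.9–5.8% at 7:3. At 8:2 it reaches about 10% with f = 0.50.

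**The case for a change.** The best argument for acting is that the remedy is free. Alternating within each group and giving a replacement the lost slot yields exactly 5:5 and 15:15, with no extra participant, blood or test. The sponsor chose alternation, so it evidently regards order as worth controlling, and 10 volunteers leave little room for avoidable imbalance. Needle order is not among the items that section 8.2 lists for recording, and section 8.7 destroys the data of those withdrawn. At 8:2, false positives could also rise.

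What stands is that the text is silent on both points and that an exact balance is preferable. The rest is weaker. The 8:2 split has probability 0.065, and only under a shared list with random mixing; the 10% error rate also needs the largest assumed order effect. The lowest power figure, 51%, combines that effect with a 7:3 split and the unfavourable direction. The concern over destroyed data is slight: in an alternating sequence a lost slot can be read from its neighbours, and section 8.7 keeps the reason for withdrawal on the case report form.

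**Conclusion.** No change to the plan is needed. The protocol leaves an allocation detail unstated; it does not set a wrong rule. Volunteers come through posters and post natal women through the pre-operative clinic, the quotas are separate, and each group is analysed alone. Staff running this would most naturally keep one alternating list per group, and nothing in the protocol prevents that.

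On that reading, one or two volunteer losses at or after phlebotomy give at worst 6:4, and the same losses in the post natal group at worst 16:14. The bias is then at most 20% and 6.7% of an order effect that the documents do not show and that the use of separate veins may reduce. Average power in the volunteers at 6:4 is within 0.1 point of 5:5. The paired, counterbalanced comparison would still support a sound conclusion.

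These sizes rest on a back-solved SD, normal differences, a two-sided signed-rank test and assumed order effects. The conclusion would weaken only if volunteers were mixed at random into one shared list and a large order effect existed. The documents support neither.

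### Needle order follows a predictable, unconcealed alternation; in this paired design the likely bias is small, but a concealed random order within each group would remove it at almost no cost.

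*Combined protocol and SAP*

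**What the plan says.** Section 8.4, although headed as randomisation, contains none: "We will alternate which needle is used first between patients". Section 6.1 repeats the rule: "We will alternate between patients with regards to which needle will be used first during phlebotomy". Neither section names a random sequence, a list holder, concealment or blinding. The plan does not say whether the alternation follows the order of enrolment or of blood sampling, or whether it runs within each group or across both. Sections 8.7 and 11.5 provide for replacing withdrawn participants and spurious data, but not for the needle order that the replacement takes.

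The comparison is within person. Section 8.4: "All participants will have a paired set of bloods taken with a hypodermic needle and the new one way valve filter needle". Section 6.1: "The punctures will be from separate veins for each of the two needles". Section 11.1 names the outcome, "The primary outcome for this study is change in time to initiate clot formation, as measured by the R time using thromboelastography", and the analysis, "As subjects are to be exposed to both study limbs the data collected will be analysed using paired tests for statistical differences", using non-parametric tests and no term for order. It adds: "There is no plan to compare non-pregnant and post natal groups, only the within group differences".

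On timing, section 6.1 recruits pregnant women at the pre-operative clinic and samples them on day 2 after caesarean section. Volunteers answer posters. Section 4 says of the first group: "The post natal population would only require one additional venepuncture with the new one-way valve needle as they would already be having bloods taken".

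**The concern.** A strictly alternating sequence is fully predictable, and the person drawing the blood can see which needle is in use. Staff who know the last order therefore know the next, and where more than one person is available they can choose who fills the slot. Section 4 makes the new needle the extra puncture for post natal women, which could give staff a practical reason to prefer one order for some of them. That motive is an inference; the plan does not state it.

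Alternating the order is meant to stop a difference between first and second draws from being read as a difference between needles. That works if the people in the two orders respond alike to being drawn first or second. If people with a larger first-to-second-draw effect collect in one order, part of that effect enters the needle estimate. An order term in the analysis would not remove it, because the imbalance lies in who received each order.

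**Working it through.** **Inputs from the documents.** Target effect: 25% reduction in R time; alpha 5%; power 80%; n = 10 non-pregnant and 30 post natal (11.2, 11.3). The SD of the paired differences and the sidedness of the test are not given. No draw-order effect is given.

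**The plan's own figure.** Without the SD, n = 10 and n = 30 cannot be reproduced, only back-solved. With n = ((1.960 + 0.842) × SD / 25)², two-sided:
- n = 10: SD = 25 × √10 / 2.802 = 28.2% of mean R (25.1% by the paired-t calculation)
- n = 30: SD = 25 × √30 / 2.802 = 48.9% (47.2% by paired t)

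These are implied values used for scale, not evidence of an error. The paired-t values are used below.

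**Bias formula.** Let d = new minus standard, δ the needle effect, and π the second draw minus the first. Order 1 has the new needle second, so its mean d is δ + π1. Order 2 has it first, so its mean d is δ − π2. Over n1 and n2 participants:

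bias = (n1π1 − n2π2) / (n1 + n2), which is (π1 − π2)/2 when n1 = n2.

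Averaging the two order-specific means, as an order-adjusted analysis does, gives δ + (π1 − π2)/2, the same bias. A participant's own R level does not appear, and π1 = π2 gives zero.

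**Simulation with equal orders, no needle effect, two-sided signed-rank test (8,000 runs each; effects in % of mean R).**

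| Scenario | Bias | Type I, n=10 | Type I, n=30 |
|---|---|---|---|
| R level differs by 40 between orders, no order effect | about 0 | 4.9% | 5.2% |
| Same, plus a common order effect of 10 | about 0 | 3.5% | 4.2% |
| Order effects 12 vs 8 | 2 | 3.8% | 4.6% |
| Order effects 15 vs 5 | 5 | 6.8% | 8.2% |
| Order effects 20 vs 0 | 10 | 15.5% | 18.4% |

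So selection alone does nothing. Selection matters only when it is linked to unequal order effects.

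**A steering model (assumed).** Suppose 30% of participants are difficult to bleed and have a draw-order effect c, and the rest have none. Staff pick the better suited of two available people at every slot. The shares of difficult participants in the two orders are then
- h1 = 1 − 0.7² = 0.51
- h0 = 0.3² = 0.09

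bias = c(h1 − h0)/2 = c × 0.42/2 = 0.21c.

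| c (% of R) | Bias (points) | Share of 25% effect | Type I, n=30 | Type I, n=10 |
|---|---|---|---|---|
| 10 | 2.1 | 8% | 5.1% | 5.2% |
| 20 | 4.2 | 17% | 7.2% | 6.0% |
| 30 | 6.3 | 25% | 9.4% | 7.6% |

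These are from 6,000 runs per cell. A separate run gave 5.4%, 7.4% and 10.1% at n = 30, and 5.2%, 6.6% and 8.0% at n = 10, which agrees within simulation error. Without steering, bias is about zero and type I error is 3.6–5.3%. Steering at half strength halves the bias: c = 20% then gives 2.1 points.

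Picking from two people is not the arithmetic limit. If every difficult participant fell in one order, h1 = 0.60 and h0 = 0, so bias = 0.30c, or 3, 6 and 9 points.

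**The case against.** The strongest reply is that this borrows a selection-bias argument from parallel-group trials. Here the sequence decides only the order of two draws in the same person. Differences between participants cancel within the pair, and balanced orders cancel a shared order effect. Bias needs three things together: a real draw-order effect on R time, one that varies between people, and steering that follows that variation. The documents give evidence of none of them. Separate veins make a local carry-over less obvious, and nothing describes a pool of waiting candidates. At c = 10% the type I error is essentially nominal even with steering at every slot. The largest figures need a 30% draw-order effect, which exceeds the 25% effect the study seeks.

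Most of this stands, and it sets the weight of the point. It does not show that the bias is zero: the plan offers no evidence that the order effect is uniform, and a concealed random order removes the need for that argument.

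Two stronger readings are tempting. A reader might infer that the next order is known before a participant is approached and consents. That could be so for volunteers, but it is not established for post natal women, who make up 30 of the 40. They are recruited before surgery and sampled on day 2, so if alternation follows sampling order their slot is not fixed at consent. A reader might also infer that equal numbers in each order give no protection. They do protect against any order effect common to all; they fail only for effects that differ between the people in the two orders.

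**Conclusion.** The concern holds as a minor one. The order is predictable and unconcealed, and the plan leaves open what the alternation follows, whether it runs within each group, and which order a replacement takes. The possible bias is (π1 − π2)/2. Under assumed steering at every slot, with effects of 10–30% of R time in 30% of participants, it is about 2–6 percentage points, with type I error about 5–9% (up to about 10% in the repeat run). Weaker steering or a more uniform order effect brings it towards zero.

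The order effects, the 30% share and the steering are all assumptions, and the SDs are back-solved from the plan's sample sizes. The documents do not show that steering is likely or that the result would be materially wrong. The case for change is that the remedy is nearly free and makes this bias zero in expectation.

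**What to change.** In sections 6.1 and 8.4, replace the alternation with text to this effect:

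*Needle order is assigned from a computer-generated random list in small permuted blocks of varying size (2 and 4), separately for the post natal group (target 15:15) and the volunteer group (target 5:5). The list is prepared by a colleague not involved in recruitment or phlebotomy and held in sequentially numbered sealed opaque envelopes. Each assignment is opened only after consent and the final eligibility check, immediately before the first puncture. The assigned order and the order actually used are recorded on the CRF. A participant recruited as a replacement under 8.7 or 11.5 takes the order of the participant replaced, revealed in the same way.*

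Opening the assignment at the first puncture also removes the ambiguity over enrolment or sampling order, and separate lists settle whether the sequence runs within groups. The paired comparison in 11.1 need not change.

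Cost: one short list and about 50 envelopes, with no extra participants, samples or visits. The downside is that an incomplete last block could leave the orders unequal by one or two participants. With a common order effect of 10% of R, a 6:4 split gives (6 × 10 − 4 × 10)/10 = 2 points and a 16:14 split gives (16 × 10 − 14 × 10)/30 = 0.7 points in that realised sample. Choosing block lengths that sum to 10 and 30, together with the replacement rule, keeps this to a minimum.
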